6.1.6 DOSE ADJUSTMENTS/MODIFICATIONS/DELAYS

Patients will be treated at a starting dose of fedratinib 400 mg PO daily, unless they require co-administration with a strong CYP3A4 inhibitor, in which case, fedratinib dose will be reduced to 200 mg PO daily (see section 7.5). There will be no dose escalation above the 400 mg PO daily dose. Dose interruptions and modifications should occur according to the US Package Insert and protocol-defined guidelines and, when feasible, this decision should be after discussion with the study PI. Adverse events that have a clear alternative explanation or transient (≤ 72 hours) abnormal laboratory values without associated clinically significant signs or symptoms may be exempt from dose reduction rules. Hematologic AEs that precipitate dose interruptions should be monitored for recovery for at least every 7 days, if feasible.

Guidelines for Management of Gastrointestinal Adverse Events:

Gastrointestinal adverse events, specifically nausea, vomiting and diarrhea, are commonly associated with fedratinib treatment and require multifaceted management using dose adjustment, active treatment or prophylaxis with anti-emetics, and monitoring. GI symptoms generally start in the first treatment cycle but typically improve within 6-8 weeks on fedratinib treatment.

Management of Nausea and Vomiting

Management of nausea and vomiting during treatment with fedratinib will be done according to the following steps:

- Patients will be provided management instructions (including when to contact the study site) before the start of treatment.

- In order to mitigate for nausea and vomiting events, it is recommended to take fedratinib with food during an evening meal. It is highly recommended to use anti-nausea/vomiting treatment prophylactically according to local practice for the first 8 weeks of treatment (eg, ondansetron). If dimenhydrinate or other muscarinic receptor antagonists are used for nausea and vomiting, administer these agents in the evening to minimize drowsiness and other potential neurological AEs.
- Hold / reduce the dose of fedratinib
- Hospitalization may be indicated for Grade 3 or higher nausea or vomiting or events that persist
- For medications that are administered for prophylactic use of nausea and vomiting, if no clinically significant nausea and vomiting occurs during the first 8 weeks of fedratinib treatment, consider weaning the patient off these medications

Management of Diarrhea

Management of diarrhea during treatment with fedratinib will be done according to the following steps:

- Patients should have loperamide available at home and should be provided with diarrhea management instructions (including when to contact the study site) before the start of treatment.
- Loperamide should not be given as prevention in case the patient does not experience diarrhea.
- Treat with loperamide as per local practice at the onset of diarrhea. Consider starting loperamide at a 4 mg loading dose and then 2 mg after each diarrheal bowel movement without exceeding 16 mg/24 hours.
- Dietary modifications including adequate hydration, avoidance of lactose-containing foods and alcohol, small meals with rice, bananas, bread, etc.
- Hold / reduce the dose of fedratinib.
- Hospitalization may be indicated for Grade 3 or higher persisting diarrhea.
- Management of nausea, vomiting and diarrhea will be assessed during the patients visit.

Guidelines for Management of Encephalopathy:

A potential case of WE is a medical emergency. Screening for WE and management of potential cases of WE during treatment with fedratinib will be done according the following steps:

Clinical and Cognitive Assessment

Interval history: including a review of the patient's history for confusion, memory problems, vision problems (e.g., double vision) as well as poor nutrition, signs and symptoms of malabsorption, and alcohol use

- Physical examination: including assessment for abnormal eye movements, cerebellar abnormalities and body weight (weight loss compared to previous examination or patient history)

Management of Potential WE

In case of signs or symptoms that may indicate WE:

- Hold fedratinib until WE is ruled out
- Obtain sample for thiamine level
- Empirically start thiamine supplementation
- Report the event as an AESI to the Sponsor
- Obtain a neurological consult

- Perform a brain MRI
- If WE is confirmed, discontinue fedratinib permanently

Thiamine Monitoring and Correction

Thiamine levels (for whole blood) will be monitored and thiamine supplementation will be administered to all patients with thiamine levels below the normal range.

- Thiamine levels are assessed at screening and need to be corrected and retested before starting fedratinib treatment (see inclusion criteria)
- While on treatment with fedratinib, thiamine levels are assessed as clinically indicated
- In case a patient is on thiamine supplementation, thiamine levels should be assessed in a fasting state for thiamine supplementation and thiamine given after the blood draw
- In case a thiamine level result is below normal, the site will contact the patient as soon as possible to start supplementation as described below.
- For thiamine levels below the normal range but ≥ 30 nM/L without signs or symptoms of WE:
- Supplementation with a minimum daily dose of 100 mg of oral thiamine must be started
- In case the results were obtained by a local laboratory, report the event as an Adverse Event of Special Interest (AESI).
- For thiamine level < 30 nM/L with or without signs or symptoms of WE:
- Immediate treatment with thiamine (preferably IV) at therapeutic dosages eg, IV infused over 30 minutes 3 times daily for 2 to 3 days or alternatively IM in equivalent doses according to local standard of care
- This will be followed by 250 mg to 500 mg IV thiamine infused once a day for 3 to 5 days or alternatively IM in equivalent doses according to local standard of care
- And then continue at an oral minimum daily dose of 100 mg thiamine for at least 90 days
- Fedratinib must be held until thiamine levels are restored to normal range.
- Thiamine supplementation should be administered as a thiamine only formulation.
- If thiamine levels are low, ensure that magnesium levels are normal or corrected if low

Guidelines for Interruption and Restarting of Study Drug

Chemistry		
Adverse Event	Trigger	Action Taken
ALT and/or AST elevation	Grade 2	
 • Continue study drug • Monitor LFTs at least weekly until \leq Grade 1 or baseline • If Grade 2 elevation lasts ≤ 14 days, no action required. • If Grade 2 elevation lasts > 14 days, interrupt drug, monitor LFTs at least weekly, and: 
 ○ If resolved within 14 days after interruption, resume study drug at the same dose, monitor LFTs at least weekly during the next month and according to the protocol schedule thereafter ○ If LFTs do not resolve to \leq Grade 1 or baseline within 14 days after interruption lasts, discuss with study PI.
	Grade 3 or 4	
 • Complete a coagulation profile on the patient. • Interrupt study drug and monitor LFTs at least weekly until \leq Grade 1 or baseline: 
 ○ If resolved within 14 days after interruption, patient may resume study drug at next lower dose.

		
 ○ If LFTs do not resolve to \leq Grade 1 or baseline within 14 days after interruption, discuss with study PI. • Carefully examine patient's concomitant medications for those that may contribute to LFT elevations. Hold those medications or switch to an alternative; consult study PI if needed. • In the case of recurrent grade ≥ 3 ALT and/or AST elevation, study drug should be discontinued.
Amylase/Lipase Elevation	Grade 2	
 • Continue study drug • If Grade 2 elevation lasts > 14 days, interrupt drug, monitor amylase/lipase at least weekly, and: 
 ○ If resolved within 14 days after interruption, resume study drug at the same dose, monitor amylase/lipase at least weekly during the next month and according to the protocol schedule thereafter • If amylase/lipase does not resolve to \leq Grade 1 or baseline within 14 days after interruption lasts, discuss with study PI.
	Grade 3 or 4	
 • Interrupt study drug and monitor amylase/lipase at least weekly until \leq Grade 1 or baseline: 
 ○ If resolved within 14 days after interruption, patient may resume study drug at next lower dose. ○ If amylase/lipase do not resolve to \leq Grade 1 or baseline within 14 days after interruption, discuss with study PI. • Carefully examine patient's concomitant medications for those that may contribute to amylase/lipase elevations. Hold those medications or switch to an alternative; consult study PI if needed.
Creatinine elevation	Grade 3 or 4	
 • Interrupt study drug for up to 2 weeks (≤ 14 days) and monitor creatinine at least weekly until \leq Grade 1 or baseline. • Carefully examine patient's concomitant medications for those that may contribute to creatinine elevation. Hold those medications or switch to an alternative; consult study PI if needed 
 ○ If deemed unrelated to study drug, resume study drug at same dose ○ If assessed as at least possibly related to study drug, resume at next lower dose; monitor as clinically indicated. • If creatinine does not resolve to \leq grade 1 or baseline within 14 days after interruption, discuss with study PI. Dose reduction to 200 mg daily should be considered in patients with severe renal impairment (creatinine clearance of 15 mL/min to 29 mL/min).

Hematology		
Thrombocytopenia	Grade 4 or Grade 3 with bleeding	
 • Hold until resolved to $> 50 \times 10^9/L$ or baseline, if baseline was lower than $50 \times 10^9/L$. • Restart dose at 100 mg daily below last given dose. • If grade 4 thrombocytopenia persists for > 14 days, then discontinue study drug.
Neutropenia	Grade 4	
 • Interrupt dose until ANC $> 1.0 \times 10^9/L$. Restart dose at 100 mg daily below the last given

		
dose.
 
 If grade 4 neutropenia persists for > 14 days, discontinue study drug.
--	--	--

Other Toxicities	
Any Grade 1 or Grade 2	Continue study drug treatment and treat the toxicity; monitor as clinically indicated
Any grade 3 toxicity, if clinically significant and not manageable by supportive care	
 Interrupt study drug up to 2 weeks (14 days); until toxicity resolves to ≤ Grade 1 or baseline. Resume study drug at same dose. If assessed as at least possibly related to study drug, resume at next lower dose; monitor as clinically indicated
Any recurrent Grade 3 toxicity at 100 mg daily dose (lowest dose allowed on study) that is at least possibly related to study drug	
 Discontinue study drug and follow-up per Protocol. Exceptions require approval of study PI.
Any other non-hematologic Grade 4 toxicity	
 Discontinue study drug and follow-up per protocol
New red blood cell (RBC) transfusion requirement	
 Dose reduction should be considered in patients who become newly dependent upon RBC transfusions.

Dose reductions will be made in increments of 100 mg with 100 mg daily being the lowest dose to be administered on study. Any toxicity that occurs at a dose level of 100 mg daily that would require a dose reduction will result in discontinuation of study drug unless otherwise approved by the study PI.

Dose increases can occur after a dose reduction if toxicity has remained ≤ 1 or at baseline for ≥ 28 days. Dose increases will be made in increments of 100 mg daily may only occur once per cycle. Dose levels can only be tried on three occasions.

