2.3 POTENTIAL RISKS AND BENEFITS

2.3.1 KNOWN POTENTIAL RISKS

According to the US fedratinib package insert, fedratinib has been used to treat 608 patients with either MPNs or solid tumors. The safety profile of the drug is consistent across studies with the most common adverse events (AEs) being hematologic and gastrointestinal (GI). The most common hematologic AEs are anemia and thrombocytopenia. These events can be managed by dose modification, including dose interruption and other supportive treatments. The most common GI events are diarrhea, nausea, and vomiting. Gastrointestinal events are generally Grade 1 to 2, but Grade 3 to 4 events have occurred and have led to discontinuation of treatment. These events commonly occur at the highest frequency in the first two cycles. Prophylactic anti-emetic therapy (e.g., 5-HT₃ receptor antagonists) during fedratinib treatment should be considered. Diarrhea should be treated with anti-diarrheal medications promptly at the first onset of symptoms. Common laboratory findings include increased alanine aminotransferase (ALT), increased aspartate aminotransferase (AST), increased amylase, increased lipase, and creatinine increased. These events are primarily asymptomatic and Grade 1 to 2 in severity. Recommendations for monitoring and dose modifications are included in the protocol.

Serious and fatal encephalopathy, including Wernicke's, was reported in patients taking fedratinib. Serious cases were reported in 1.3% (8/608) of patients treated with fedratinib in clinical trials and 0.16% (1/608) of cases were fatal.

Seven out of the 8 patients were taking fedratinib at 500mg daily prior to the onset of neurologic findings and had predisposing factors such as malnutrition, gastrointestinal adverse events, and other risk factors that could lead to thiamine deficiency. This dose will not be assessed in the current study. Most events resolved with some residual neurological symptoms including memory loss, cognitive impairment, and dizziness. In a solid tumor study, one patient with head and neck cancer, brain metastasis, difficulty eating and weight loss had a fatal outcome.

Despite these potential risks, we believe the investigation of fedratinib in patients with MDS/MPN and CNL is worth pursuing since these diseases have poor prognoses, lack treatment options, and the preclinical and clinical evidence suggests patients have a high potential to benefit.

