7.1.11 Vital Signs

The investigator or qualified designee will take vital signs at screening and on day 1 of cycles 1-6. Vital signs should include temperature, pulse, respiratory rate, and blood pressure. Weight is required to be measured on cycle 1 day 1.

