7.3.3 ON-TREATMENT VISITS

7.3.3.1 Cycle 1; Day 8, 15, 22 and Cycle 2, Day 15)

- Focused physical exam
- Assess and record symptoms
- CBC with differential
- Chemistry profile (sodium, potassium, chloride, creatinine, BUN, total protein, albumin, AST, ALT, alkaline phosphatase, total bilirubin, calcium, CO2)
- LDH, amylase, lipase

7.3.3.2 Cycle 2-3; Day 1

- Record vitals
- Focused physical exam
- Assess and record symptoms
- CBC with differential
- Chemistry profile (sodium, potassium, chloride, creatinine, BUN, total protein, albumin, AST, ALT, alkaline phosphatase, total bilirubin, calcium, CO2)
- LDH, amylase, lipase
- Thiamine level to be checked on Cycle 2, Day 1
- Assess TSS with MPN SAF
- Assess PGIC

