7.3.7 SCHEDULE OF EVENTS TABLE

Procedures	Screening	Enrollment/Baseline Cycle 1, Day 1	Cycle 1*, Day 8, 15, 22 (+/- 5 days)	Cycle 2, Day 1 (+/- 7 days)	Cycle 2, Day 15 (+/- 5 days)	Cycle 3, Day 1 (+/- 7 days)	Cycle 4, Day 1 Week 12 Assessment (+/- 7 days)	Cycle 5, Day 1 (+/- 7 days)	Cycle 6, Day 1 (+/- 7 days)	Cycle 7, Day 1 Week 24 Assessment (+/- 14 days)	Subsequent Visits (Every 3 cycles) (+/- 14 days)	End of Treatment Visit (+/- 7 days from study drug completion) ^e
Informed consent	X											
Demographics	X											
Medical history	X											
Concurrent meds	X		X ----- X									
Fedratinib dispensed ^d		X	X	X	X	X	X	X	X	X	X	
Investigational Drug Diary Provided		X		X		X	X	X	X	X	X	
Physical exam	X	X	X	X	X	X	X	X	X	X	X	X
Vital signs	X	X	X	X	X	X	X	X	X	X	X	X
Weight		X										
Performance status (ECOG)	X	X										
CBC w/diff, plt's	X	X	X	X	X	X	X	X	X	X	X	X
Metabolic panel ^a	X	X	X	X	X	X	X	X	X	X	X	X
Uric acid, magnesium, phosphorous	X											
Amylase, lipase	X	X	X	X		X	X			X		
LDH	X	X		X		X	X	X	X	X	X	X
Folic acid, Vitamin B12	X											
Thiamine	X	X		X			X			X	X	
CRP		X					X			X	X	
Serum Pregnancy test ^b	X											
Adverse event evaluation			X ----- X									
Spleen Imaging	X						X			X	X ^c	
MPN SAF TSS	X	X		X	X	X	X	X	X	X	X	
PGIC				X	X	X	X	X	X	X	X	
MDS/MPN Response Assessment							X			X	X ^c	
Bone Marrow Biopsy/Aspirate	X									X		
Bone marrow aspirate for correlatives	X									X		

Peripheral Blood Draw for correlatives	X						X			X		
Cytogenetics	X											
Next Generation Sequencing	X											
a: Albumin, alkaline phosphatase, total bilirubin, CO2, BUN, calcium, chloride, creatinine, glucose, potassium, total protein, AST,ALT, sodium, b: Serum pregnancy test (women of childbearing potential). c: Spleen imaging and MDS/MPN response criteria to be performed every 24 weeks +/- 28 days (6 cycles) after week 24 d: See section 7.2.3 and 7.2.4 for details regarding specimen preparation, handling, and storage * Cycle length = 28 days												

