8.4.4 EVENTS OF SPECIAL INTEREST

An adverse event of special interest (AESI) is one of scientific and medical interest specific to understanding of the Investigational Product and may require close monitoring of patients and rapid communication by the investigator to the study PI. AESIs will additionally be reported back to Celgene/BMS. An AESI may be serious or non-serious. The rapid reporting of AESIs allows ongoing surveillance of these events in order to characterize and understand them in association with the use of this investigational product

The following are considered to be Adverse Events of Special Interest (AESIs):

- Wernicke encephalopathy (WE) or suspected cases of WE associated with thiamine levels below normal range.
- Thiamine levels below normal range with or without signs or symptoms of WE
- Cardiac failure or cardiomegaly

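### Body weight is part of Wernicke screening in 6.1.6 but is scheduled only at C1D1, and the 8.4.4 AESI list is narrower than 6.1.6 on suspected Wernicke's encephalopathy

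*Combined protocol and SAP*

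**What the plan says.** **Weight.** The encephalopathy guidance in protocol section 6.1.6 covers screening during treatment as well as the handling of suspected cases. Its physical examination includes eye movements, cerebellar signs and "body weight (weight loss compared to previous examination or patient history". Section 7.1.11 states "Weight is required to be measured on cycle 1 day 1" and does not count weight among the vital signs. Section 7.1.10 accepts problem-focused examinations outside screening, C4D1 and C7D1. The C1D1 list in 7.3.2.1 names weight. The on-treatment lists in 7.3.3, beginning with "Cycle 1; Day 8, 15, 22 and Cycle 2, Day 15", do not. The weight row in the 7.3.7 table has one mark, at C1D1.

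**AESI reporting.** For a clinical picture that could be WE, 6.1.6 says "Report the event as an AESI to the Sponsor" and sets no condition on thiamine; the thiamine sample is ordered in the same list of steps. For thiamine below normal but at least 30 nM/L without WE signs, 6.1.6 says "In case the results were obtained by a local laboratory, report the event as an Adverse Event of Special Interest (AESI". Its steps for thiamine below 30 nM/L deal with treatment and holding the drug and contain no AESI instruction. Section 8.4.4 is the formal list. It has three items: WE, or "suspected cases of WE associated with thiamine levels below normal range"; any below-normal thiamine, whether or not WE is suspected; and cardiac failure or cardiomegaly.

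**The concern.** One section orders a check that the visit schedule does not carry. Sites usually work from the schedule, so a check that appears only in management guidance is easily missed. Section 2.3.1 names malnutrition and gastrointestinal adverse events among the factors that preceded the serious encephalopathy cases. Of the gastrointestinal events it says "These events commonly occur at the highest frequency in the first two cycles". A measured weight is most useful in that period, and none is scheduled after the first dose.

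On AESIs, a site using only 8.4.4 could leave out a suspected WE case with normal thiamine. A site using only 6.1.6 could leave out a thiamine result below 30 nM/L without WE signs. Four sites enroll, and 10.4.4 tabulates AESIs. Uneven flagging would affect rapid reporting and possibly that table.

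**Working it through.** No statistical calculation applies. The check is a count from the 7.3.7 table and a comparison of the two sections.

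**Schedule count.** The table has 12 visit columns.
- Physical exam: marked in 12 of 12.
- Weight: marked in 1 of 12, at C1D1.
- On-treatment visits from C1D8 to C7D1: 3 (C1D8, C1D15, C1D22) + 7 (C2D1, C2D15, C3D1, C4D1, C5D1, C6D1, C7D1) = 10. All 10 have a physical exam, 0 have a weight, and 3 have thiamine (C2D1, C4D1, C7D1).
- Visits after the first dose in cycles 1 and 2: 3 + 2 = 5 of the 10.
- The column for later visits every three cycles has an exam and thiamine, but no weight.
- At C1D8, C1D15 and C1D22 the table schedules neither thiamine nor the MPN-SAF. That form's weight-loss item looks back six months, so early in treatment it cannot separate loss on drug from loss before it.

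Section 7.1.11 and the lists in 7.3 agree with the table, so the single mark is not an artefact of how the table was read.

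**AESI comparison.**

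| Situation | 6.1.6 prompts an AESI report | 8.4.4 lists it |
|---|---|---|
| Confirmed WE | Yes, since it first presents as suspected | Yes |
| Suspected WE, low thiamine | Yes | Yes |
| Suspected WE, normal thiamine | Yes | No |
| No WE signs, thiamine below normal but >= 30 nM/L | Yes, if a local laboratory | Yes |
| No WE signs, thiamine < 30 nM/L | No | Yes |
| Cardiac failure or cardiomegaly | Outside its subject | Yes |

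Suspected WE with a pending result falls under 8.4.4 once the result comes back low, so the only situation that 8.4.4 omits is the third row. The prompt in 6.1.6 is missing for the more severe thiamine band, which 8.4.4 covers. Under 7.2.1 the tests are done at the treating institution, so the local-laboratory condition would ordinarily be met. Every situation is covered by at least one section.

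**The case against.** The strongest reply on weight is that 6.1.6 already requires it and that a physical exam is scheduled at every visit. Eye-movement and cerebellar checks have no table row either. Section 7.1.11 sets a minimum and does not forbid later weights. Section 6.1.6 gives no screening frequency and accepts patient history as a comparator. All of this stands. A reader might infer that the protocol requires no weight after baseline, or that ten mandatory measurements are missing. Neither is supported: 0 of 10 describes the schedule, not breaches of a stated frequency. What remains is that the instruction is not carried into the visit schedule, and that problem-focused exams make it easier to omit.

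On AESIs, a reader might infer two competing lists that cannot both be obeyed. The documents do not support that. Section 8.4.4 is the only list, and 6.1.6 is management guidance with reporting prompts, so its silence on cardiac events is not a defect. Nor is thiamine below 30 nM/L unreportable, because 8.4.4 covers it. The recipients differ in wording, the Sponsor in 6.1.6 and the study PI plus Celgene/BMS in 8.4.4. But 8.4.2 names the lead cancer center as study sponsor and 8.4.4 adds the company as a further recipient, so this is not a conflict.

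A reader might also infer missed WE cases or lost safety data. Under 8.1.1 a laboratory abnormality that needs treatment or a dose hold is an AE, and thiamine below 30 nM/L needs both, so it is recorded even without an AESI flag. Section 8.6 expedites serious events. Seven of the eight serious cases in 2.3.1 were at 500 mg, a dose not used here. Interval history, correction of low thiamine before the first dose, as-indicated thiamine testing and recommended anti-emetic prophylaxis also remain.

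**Conclusion.** The point holds as a minor safety-consistency issue. A follow-up weight depends on the site acting on 6.1.6 because the schedule has none after C1D1. Section 8.4.4 is narrower than 6.1.6 on suspected WE without low thiamine. Within 6.1.6, the AESI prompt is attached to the milder thiamine band and absent from the more severe one.

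The practical effect arises only if a site relies on the schedule, or on one of the two sections, alone. Section 2.3.1 reports serious encephalopathy in 8 of 608 patients (1.3%), one of them fatal, but the documents do not give the number treated at each dose. No WE rate at 400 mg, and no number of missed or late cases, can be estimated. The conclusion assumes that WE screening is meant to recur during treatment, as 6.1.6 indicates without giving an interval. The primary endpoint, sample size and decision rule are not touched.

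**What to change.** 1. Add weight to 7.1.11, the 7.3.3 visit lists and the 7.3.7 table at on-treatment visits that already have a physical exam: every visit through cycle 2, then each later day 1 visit. Up to C7D1 this is 5 + 5 = 10 weighings per patient, with no new visits.
2. Change the first item in 8.4.4 to *confirmed or suspected WE regardless of thiamine level*. Leave the other two items as they are.
3. In 6.1.6, replace the AESI prompts with *report as an AESI per 8.4.4*, and drop the local-laboratory condition.

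The cost is amendment wording, a brief weighing at existing visits, and a few more AESI reports, some of which will not prove to be WE.
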